17.2 Sample Size

Approximately 120 to 200 subjects will be enrolled in this study. The sample size is based on the requirements of the final safety database for approval.

17.3 Analysis Populations

All subjects who return to the clinic on Day 1 (i.e., study baseline) and have all required baseline (before injection of study drug) assessments/procedures completed will be considered study participants. Study populations, identified and finalized before the database lock, are as follows:

Safety Population

This population is defined as all subjects who are injected with at least 1 dose of study drug. Where applicable, subject grouping will be based on the actual doses the subject received at each session and grouped into 3 groups: low dose (2,500 to 2,999 Units), medium dose (3,000 to 3,499 Units), and high dose (3,500 Units).

Intention-to-Treat (ITT) Population

This population is defined as all subjects who are injected with study drug and have at least 1 post-baseline measurement recorded in the eCRF for both USFR and CGI-C. The ITT population will be used for effectiveness analyses.

17.4 Demographic and Baseline Characteristics

Descriptive summaries of subject demographic and baseline characteristics will be presented for the safety population and ITT population. Subject characteristics will include a summary of demography, baseline disease characteristics, pre-existing medical conditions, prior therapies for the treatment of sialorrhea, as well as baseline effectiveness measures of USFR, CGI-S, PGI-S, DFSS-I, and DFSS-S.

17.5 Subject Disposition

Descriptive summaries of subject disposition will be presented for the safety population and ITT population. A detailed description of individual subject disposition will be provided in a data listing.

17.6 Safety Endpoints

Safety endpoints include adverse events and AESI, vital signs and weight, neurological exam, physical examination, dental exam, C-SSRS, and clinical laboratory tests. Adverse events will be coded using the Medical Dictionary for Regulatory Activities (MedDRA) adverse event dictionary.

For safety endpoints, records with valid data within each visit or assessment time point will be identified for initial and repeat, where applicable. The initial record will be used in statistical analysis, whereas all records will be presented in data listings. Missing or invalid data will be treated as missing for the corresponding visit or time point.

The baseline of each treatment session consists of the corresponding measurement value obtained at pre-injection of each treatment session (i.e., Day 1, Weeks 13, 26, and 39).

17.7 Statistical Methods for Safety

Frequency of treatment-emergent adverse events (TEAEs) will be calculated for each body system, by preferred term, and by treatment session, for number of subjects and proportion reporting the event and AESI. The incidence of subjects reporting TEAEs will also be reported without those TEAEs categorized as related to the primary underlying disease conditions by the Investigator. The severity of the adverse events and the relationship to study drug will be summarized for each body system and preferred term. Withdrawals due to adverse events will be summarized for each body system and preferred term. Narratives will be presented for all deaths, subjects reporting SAEs, and subjects withdrawn due to adverse events.

Vital signs and weight will be summarized descriptively for continuous variable at each pre-injection visit (i.e., Day 1, Weeks 13, 26, and 39) and at each post-injection time point of 4 weeks post-injection (i.e., Weeks 4, 17, 30, and 43), 8 weeks post-injection (i.e., Week 8, first Treatment Session only), and 13 weeks post-injection (i.e., Weeks 13, 26, 39, and 52). The change scores in weight, vital signs, and neurologic exam average score from pre-injection (i.e., Day 1, Weeks 13, 26, and 39) at 4 weeks post-injection (i.e., Weeks 4, 17, 30, and 43), 8 weeks post-injection (i.e., Week 8, first Treatment Session only), and 13 weeks post-injection (i.e., Weeks 13, 26, 39, and 52) will be analyzed, using a paired t-test where applicable, by treatment dose group defined in Section 17.3 for the safety population (i.e., low dose, medium dose, and high dose).

Neurologic exam average score will be summarized descriptively for continuous variable at baseline (Day 1, before first injection of study drug), and post-baseline Weeks 13 and 52. The change scores in neurologic exam average score from baseline at post-baseline time points will be analyzed, using a paired t-test where applicable, by treatment dose group

defined in Section 17.3 for the safety population (i.e., low dose, medium dose, and high dose).

Physical examination will be summarized for abnormal findings at pre-injection of each session and will be reported at post-injection Week 13 (i.e., Weeks 13, 26, 39, and 52), using shift tables.

Each of the three C-SSRS subscales (suicidal ideation, suicidal behavior, and intensity of suicidal ideation) will be summarized descriptively for continuous variable at each pre-injection visit (i.e., Day 1, Weeks 13, 26, and 39) and at each post-injection time point of 4 weeks post-injection (i.e., Weeks 4, 17, 30, and 43), 8 weeks post-injection (i.e., Week 8, first Treatment Session only), and 13 weeks post-injection (i.e., Weeks 13, 26, 39, and 52).

The change scores in C-SSRS subscales from pre-injection at 4 weeks, 8 weeks (first Treatment Session only), and 13 weeks post-injection will be analyzed, using a paired t-test where applicable, by treatment dose group defined in Section 17.3 for the safety population (i.e., low dose, medium dose, and high dose).

Clinical laboratory tests of hematology, chemistry, and urinalysis (specific gravity and pH) will be summarized descriptively at available visits. Qualitative analysis of laboratory tests in terms of abnormality will be performed, using the shift-table method, for individual post-screening visits. Abnormal findings of clinical laboratory tests for individual subjects will be provided by data listing.

Abnormal findings of dental exam for individual subjects will be provided by data listing.

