16.5 Neurologic Exam

A neurologic exam will be performed at screening, on Day 1 (before the first injection of study drug), and at Weeks 13 and 52. A neurologic exam will also be performed as needed at the Investigator's discretion throughout the study and, if applicable, at discontinuation from the study. The neurologic exam will consist of 9 sections to evaluate: 1) level of consciousness; 2) speech; 3) cranial nerves; 4) motor; 5) sensory; 6) coordination; 7) gait; 8) reflexes; and 9) Romberg test (Appendix H).

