16.8 Physical Exam

A complete physical exam will be performed at screening and Weeks 4, 13, 26, 39, and 52, or, if applicable, at discontinuation from the study. The complete exam will involve gross examination of general appearance; head, ears, eyes, nose and throat; skin; extremities; chest; abdomen; and lymph nodes. Cardiac and pulmonary auscultation and measurement of vital signs (see Section 16.3) and weight will also be conducted as part of the complete physical exam.

A brief physical exam, consisting of cardiac and pulmonary auscultation and measurement of vital signs (see Section 16.3) will be performed on Day 1 (before the first injection of study drug) and at Weeks 8, 17, 30, and 43. Height will be recorded at screening only.

FVC will be measured in all subjects with ALS, and in other subjects if warranted, at the discretion of the Investigator at screening, before the first injection of study drug on Day 1, at Weeks 4, 8 (as clinically warranted), and 13. Thereafter, FVC will be checked if warranted at Investigators' discretion (such as if the subject has ALS).

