Withdrawals due to adverse events will be summarized for each body system and preferred term. Serious adverse events (SAEs) (including deaths) will be listed for individual events.

Narratives will be provided for all deaths, non-fatal serious adverse events, and subjects withdrawn due to adverse events.

Vital Signs and Weight

Vital signs and weight will be summarized descriptively by treatment session at pre-injection (i.e., Day 1 and Weeks 13, 26, and 39) and at each post-injection time point of 4 weeks post-injection (i.e., Weeks 4, 17, 30, and 43), 8 weeks post-injection (i.e., Week 8 first treatment session only), and 13 weeks post-injection (i.e., Weeks 13, 26, 39, and 52). The change scores in vital signs and weight from baseline at 4 weeks, 8 weeks (first treatment session only), and 13 weeks post-injection will be summarized descriptively.

Neurologic Exam

Abnormal findings of neurological exam data will be listed, respectively, for individual subjects.

Lung Functioning Test

Findings of forced vital capacity (FVC) data will be listed, respectively, for individual subjects.

Physical Examination

A complete Physical Examination was performed at Screening, Week 4, Week 13, Week 26, Week 39, Week 52, and Early Discontinuation. A brief Physical Examination was performed at Day 1, Week 8, Week 17, Week 30, and Week 43 when body weight, height and body mass index (BMI) were recorded. If any of the Physical Examination findings were abnormal and clinically significant prior to treatment, the event was recorded as medical history, while if occurred after treatment the event was recorded as a TEAE.

Suicidality Assessment

For each treatment session, each of the three C-SSRS subscales (suicidal ideation, suicidal behavior, and intensity of suicidal ideation) will be summarized descriptively for continuous variable at each pre-injection visit (i.e., Day 1 and Weeks 13, 26, and 39) and at each post-injection time point of 4 weeks post-injection (i.e., Weeks 4, 17, 30, and 43), 8 weeks post-injection (i.e., Week 8, first treatment session only), and 13 weeks post-injection (i.e., Weeks 13, 26, 39, and 52). The change scores in C-SSRS subscales from pre-injection at 4 weeks, 8 weeks (first treatment session only), and 13 weeks post-injection will be summarized descriptively.

Dental Examination and Oral Examination

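### Protocol 17.7 gives two conflicting neurologic-exam change plans, one of which the visit schedule cannot supply, and the SAP drops both without explanation, leaving the feasible comparison with Day 1 unmade

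*Protocol*

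**What the plan says.** Protocol 17.7 (Statistical Methods for Safety) treats the neurologic exam in two consecutive paragraphs.

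- The paragraph on vital signs and weight includes "The change scores in weight, vital signs, and neurologic exam average score from pre-injection (i.e., Day 1, Weeks 13, 26, and 39"), with change taken to 4 weeks, 8 weeks (Session 1 only) and 13 weeks after each injection, "using a paired t-test where applicable", by dose group.
- The next paragraph summarises the average score "at baseline (Day 1, before first injection of study drug), and post-baseline Weeks 13 and 52" and tests change from that single baseline.

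Protocol 16.5 sets the schedule: "A neurologic exam will be performed at screening, on Day 1 (before the first injection of study drug), and at Weeks 13 and 52". It continues: "A neurologic exam will also be performed as needed at the" investigator's discretion, and the exam is also done at discontinuation. Protocol 14.3.2 to 14.6.2 make the exams at Weeks 4, 8, 17, 26, 30, 39 and 43 conditional on clinical need. Protocol 14.7 includes the exam in the early-discontinuation visit.

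SAP 2.9.2 states: "Abnormal findings of neurological exam data will be listed, respectively, for individual subjects". SAP 5.8 repeats this for the safety population. Neither section mentions an average score, a change or a shift.

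**The concern.** Long-term safety is the primary objective, and Protocol 17.6 names the neurologic exam as a safety endpoint. The protocol gives two rules for analysing it, and only one fits the visits at which it must be done. The SAP then follows neither.

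Eligible diagnoses include Parkinson's disease, ALS, stroke, cerebral palsy and brain injury, so some subjects can be expected to have abnormal findings before the first injection. A list of abnormal findings with no stated reference to Day 1 does not, as specified, separate existing deficit from new or worse deficit. At stake is the one structured comparison of neurologic status with baseline that the collected data allow.

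**Working it through.** The plan states no figure on this point, so the check is a count of visits.

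**Inputs.** Required neurologic exams (Protocol 16.5 and Table 2): screening, Day 1, Week 13, Week 52, and discontinuation where it applies. Injections: Day 1 and Weeks 13, 26 and 39. Post-injection points: 4, 8 (Session 1 only) and 13 weeks.

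**Per-session plan.** Number of contrasts = 3 (Session 1) + 3 sessions × 2 = 9.

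| Session | Contrast | Exam required at start | Exam required at end |
|---|---|---|---|
| 1 | Day 1 to Week 4 | yes | no |
| 1 | Day 1 to Week 8 | yes | no |
| 1 | Day 1 to Week 13 | yes | yes |
| 2 | Week 13 to Week 17 | yes | no |
| 2 | Week 13 to Week 26 | yes | no |
| 3 | Week 26 to Week 30 | no | no |
| 3 | Week 26 to Week 39 | no | no |
| 4 | Week 39 to Week 43 | no | no |
| 4 | Week 39 to Week 52 | no | yes |

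Both ends required: 1. One end only: 5. Neither end: 3. Check: 1 + 5 + 3 = 9. In Sessions 2 to 4: 0 of 6.

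The other 8 contrasts could be filled only from as-needed exams. Those are done when someone judges them clinically warranted, so the paired subjects would be selected, probably towards those with symptoms. Their mean change would not describe the treated population.

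**Single-baseline plan.** Day 1 to Week 13 and Day 1 to Week 52 both have required exams at each end: 2 of 2. The first covers the period after injection 1. The second is cumulative over up to 4 injections.

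**SAP.** Contrasts specified: 0. SAP 3.4 gives a reason for a different departure from the protocol (the safety and ITT populations differ by one subject), but SAP 2.9.2 and 5.8 give none for this one. SAP 2.9.2 and 5.11 already use shift tables for laboratory tests.

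**Coverage at Week 52.** Sessions 3 and 4 are marked optional in Table 2. A subject whose participation ends at Week 26 has no required neurologic exam at that visit. Unless the discontinuation visit is applied, such a subject may have no required exam after the second injection.

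**The case against.** Four points deserve weight.

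1. *The SAP governs.* Protocol 17 leaves detailed methods to the SAP, and the SAP has no per-session neurologic contrast. The count of 1 in 9 therefore describes an analysis that will not be run. This stands as far as it goes: the schedule mismatch does not threaten any SAP output. It does not explain why the feasible Day 1 comparison was dropped too.

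2. *The protocol does contain a workable plan.* A reader might infer from the per-session sentence that the protocol has no feasible neurologic analysis. The next paragraph of 17.7 shows otherwise. The protocol fault is an inconsistency, and the qualifier "using a paired t-test where applicable" softens the test further, although it does nothing about the selection behind as-needed exams.

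3. *Other neurologic safety output exists.* A reader might conclude that neurologic safety over repeat injections cannot be read at all. The documents do not support that. SAP 5.3, 5.4 and 5.6 report treatment-emergent events, events of special interest and distant-spread events by session. The distant-spread list includes muscular weakness, areflexia, facial palsy, dysarthria and diplopia. Protocol 16.2.1 counts exacerbation of a pre-existing condition as an adverse event. The same section, however, exempts anticipated fluctuations that are not clinically significant, so gradual change depends on investigator judgement in a study with no control arm. The tables complement the exam and do not replace it.

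4. *The listing may show more than its description.* The listing shells and the neurologic exam appendix are not in the available text. The listing could place Day 1 findings beside later ones. That is possible but unverified, and a by-subject listing would still give no summary.

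A reader might also extend the point to the physical-exam shift in 17.7, because Day 1 has only the brief exam. The SAP no longer plans that shift. SAP 2.9.2 and 5.10 send clinically significant findings to medical history if they precede treatment and to adverse events if they follow it. The point does not reach the physical exam.

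**Conclusion.** The point holds for the neurologic exam only. Protocol 17.7 contains two inconsistent plans: one supported by required exams for 1 of 9 contrasts (0 of 6 in Sessions 2 to 4), the other for 2 of 2. The SAP replaces both with a listing and gives no reason. As a result, change in the exam is not summarised, and on this schedule it could not be read separately for Sessions 2 to 4 whatever the SAP said. Neurologic safety information by session remains available through adverse events.

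This rests on three assumptions. As-needed exams are not done routinely in all subjects. A relevant share of subjects are abnormal at Day 1, which is inferred from the eligible diagnoses since the documents give no rate. The listing does no more than SAP 2.9.2 and 5.8 describe. The change is worth making because it serves the primary objective at little cost, but it does not call the study's safety evaluation as a whole into question.

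**What to change.** **Protocol 17.7.** Remove the neurologic average score from the per-session sentence and keep the paragraph on Day 1 to Weeks 13 and 52.

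**SAP 2.9.2 and 5.8.**

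- Add a comparison from Day 1 to Week 13, and from Day 1 to Week 52 or early discontinuation. Use a shift table for each of the 9 exam sections, or a change summary if the exam is recorded as a score. The choice depends on the exam form in the appendix.
- Use scheduled and discontinuation exams only, and show discontinuation exams separately from Week 52 because their timing varies.
- Report the denominator at each time point, since Sessions 3 and 4 are optional.
- Keep the listing, and flag as-needed exams in it as unscheduled.
- If the average score is to be abandoned, give the reason.

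**Cost.** Wording in both documents and one table. It needs no new exams, provided the recorded exam findings can be tabulated by section or as a score.

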17.8 Effectiveness Endpoints

Effectiveness endpoints include USFR, CGI-C, CGI-S, DFSS-I, PGI-C, PGI-S, DIS, and DFSS-S.

17.9 Statistical Methods for Effectiveness

As subjects will receive multiple single-dose injections, each single-dose injection plus its follow-up period will be considered as a treatment session. Post-injection effectiveness endpoints over each of the treatment sessions include USFR, CGI-C, CGI-S, DFSS-I, PGI-C, PGI-S, DIS, and DFSS-S at the injection visit (i.e., Day 1, Weeks 13, 26, and 39), 4 weeks post-injection (i.e., Weeks 4, 17, 30, and 43), 8 weeks post-injection (i.e., Week 8, first Treatment Session only), and 13 weeks post-injection (i.e., Weeks 13, 26, 39, and 52). The pre-injection time points are Day 1 and Weeks 13, 26, and 39 for each of the consecutive treatment sessions. Missing post-injection measurements will not be imputed, whereas missing measurements at the pre-injection of each treatment session will be imputed by the site-specific average of those subjects who receive the treatment at the corresponding treatment session.

For each treatment session, effectiveness analysis of the treatment response will be performed on USFR change from pre-injection, CGI-C, CGI-S, PGI-C, PGI-S, and DIS change from pre-injection, DFSS-I change from pre-injection, and DFSS-S change from

pre-injection at each of the post-injection time points for the ITT population, using a paired t-test. The ITT population will be grouped into three groups by the actual doses the subject received at each session as the following: low dose (2,500 to 2,999 Units), medium dose (3,000 to 3,499 Units), and high dose (3,500 Units).

In addition, the proportion of treatment responders will be reported for the CGI-C and PGI-C at both pre-injection and post-injection time points over each treatment session. Before the analysis, the CGI-C and PGI-C variables will be dichotomized into 2 categories, with “very much improved” and “much improved” into 1 category and the remaining levels in the other category.

18 ETHICS

This study will be conducted according to Good Clinical Practice (GCP) guidelines; US Code of Federal Regulations (CFRs) dealing with Protection of Human Subjects (US 21 CFR Part 50) and Institutional Review Boards (US 21 CFR Part 56); the Nuremberg Code; and the Declaration of Helsinki, revised version of Seoul, October 2008 (in compliance with the FDA’s guidance).

18.1 Ethics Review

The US FDA regulates studies of drugs, biologics, and medical devices. Consequently, these studies are subject to regulations and guidance issued by the FDA and are included in the following parts of the US CFR and guideline document:

- 21 CFR Part 11 - Electronic Records; Electronic Signatures;
- 21 CFR Part 50 - Protection of Human Subjects;
- 21 CFR Part 56 - Institutional Review Boards (IRBs);
- 21 CFR Part 312 - Investigational New Drug (IND) Application; and
- ICH E6: Good Clinical Practice.

Copies of these materials can be downloaded from the FDA’s website at www.fda.gov.

The purpose of these regulations, legal obligations, and guidelines is to define the standards and principles for the proper conduct of clinical trials that have been developed by the medical, scientific, and regulatory communities. They are not intended to impede or restrict clinical research.

18.2 Ethical Conduct of the Study

As a Principal Investigator, you agree to conduct this study in accordance with the ethical standards defined within GCP in order to ensure that:

- Human subjects are provided with an adequate understanding of the possible risks of their participation in the study, and that they have a free choice to participate or not;
- The study is conducted with diligence and in conformance with the protocol in such a way as to ensure the integrity of the findings; and

- The potential benefits of the research justify the risks.

Solstice Neurosciences is the Sponsor of the IND. The Sponsor is responsible for the following:

- Selecting qualified Investigators;
- Providing Investigators with the information they need to properly conduct an investigation (i.e., protocol training);
- Ensuring proper monitoring of the investigation;
- Ensuring that the study is conducted according to the general investigational plan and protocols contained in the IND;
- Maintaining the IND; and
- Ensuring that FDA and all participating Investigators are properly informed of significant new information regarding adverse effects or risks associated with the drug being studied.

18.3 Study Conduct

This study will be conducted in accordance with the Sponsor's standards that meet GCP regulations. These standards reflect the following guidelines:

- GCP: Consolidated Guideline (International Conference on Harmonization [ICH] Technical Requirements for the Registration of Pharmaceuticals for Human Use, May 1996);
- US CFR dealing with clinical studies (21 CFR Parts 50, 54, 56, 312, and 314);
- HIPAA of 1996 (45 CFR Part 164); and
- Declaration of Helsinki, revised version of Seoul, October 2008.

18.4 Institutional Review Board Approval

Before initiating the study, the Principal Investigator will obtain written approval from a central IRB or the Principal Investigator's IRB (if such site is not eligible to use a central IRB) that complies with the requirements specified in GCP Title 21 Part 56 of the US CFR relating to IRBs and the ICH Guideline for GCP (E6). Study drug will not be shipped until IRB approval is obtained. Should changes to the study protocol become necessary, protocol amendments (provided by the Sponsor) will be submitted in writing to the central IRB (and the Principal Investigator's IRB) for IRB approval before implementation. In addition, the Principal Investigator's IRB must approve all site-specific advertising used to recruit subjects for the study. If the duration of the study is greater than 1 year, re-approval by the IRB must be obtained annually (or at more frequent intervals if required by the IRB).

Progress reports will be submitted to the central IRB annually or at a frequency requested by the IRB. You must also provide progress reports to your IRB, as well as any SAE reports from your study site. You are also responsible for providing the IRB with reports of any SAEs from any other study conducted with the study drug. The latter will be provided by the

Sponsor. If you are using the central IRB selected by the Sponsor, safety updates (except SAEs occurring at your site) will be reported directly to the central IRB on your behalf.

